*As described in Section 3.3.1, the 10 mg/kg BID dose is seen as the advisable dose regimen to be able to reach the targeted, higher exposure levels that may lead to an increase in efficacy. The total daily dose in this study will not exceed 2000 mg. This maximum dose of 2 g/day forms the basis of the technical IMP specifications in the drug manufacturing process and cannot be exceeded for this reason. Therefore, all patients with a body weight >100 kg will receive a dose of 1000 mg BID.*

*During clinical development of olesoxime, over 900 healthy volunteers and patients have been exposed to olesoxime, with a daily dose ranging between 50 mg to 1000 mg and treatment duration up to 43 months. Olesoxime has shown to be well tolerated at all tested dose regimens including co-administration with riluzole or beta-interferons. Atrioventricular conduction abnormalities observed in dogs have not been observed to date in humans. To date, there are no identified risks with olesoxime therapy in humans.*

*As mentioned above, the accumulating data from the open-label extension study BN29854 continues to demonstrate that olesoxime is generally safe and well tolerated at the dose assessed, with a safety profile comparable to the placebo group of Study TRO19622CLEQ1275-1 (see Section 1.2.4) (Muntoni et al. 2017).*

*From a safety perspective, the 10 mg/kg BID dose appears appropriate as the expected exposure at 10 mg/kg BID is covered by chronic preclinical toxicity studies. Nevertheless, considering preclinical findings of arrhythmias observed in the 39-week toxicity studies in dogs that started at the lowest dose (50, 250, and 1000 mg/kg/day) and in order to ensure the safeguards of patients participating in this study, a 24-hour Holter ECG monitoring will be performed prior to the dose increase to 10 mg/kg BID and 4 weeks later when steady-state is expected to be reached.*

*Based on the existing preclinical data, clinical data (including analysis of the efficacy data from the completed trials and results of the BP39378 study), the safety profile of the 10 mg/kg QD dose observed to date, and the results of the BP39378 study, the Sponsor considers the benefit–risk balance to be positive for the continuation of the olesoxime development program and for an olesoxime dose increase to 10 mg/kg BID.*

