### Schedule of Assessments (cont.)

- l Only assessed in patients aged 9–17 years at Visit 1 and annually thereafter.
- m For a list of all safety laboratory assessments, please refer to Section 4.4.8.
- n For patients aged 6–17 years, *includes* thyroid hormones (free thyroxine T4 and thyroid-stimulating hormone); and for patients aged 12–17 years or younger who have menses, also includes estradiol, follicle-stimulating hormone, *and* luteinizing hormone. Hormone assessments should occur every 12 months.
- o Urine pregnancy tests will be performed at all visits. If a urine pregnancy test is positive, it must be confirmed by a serum pregnancy test.
- p Includes dipstick (pH, specific gravity, glucose, protein, ketones, blood). If deemed necessary for further investigation, the treating physician can request microscopic examination (sediment, RBCs, WBCs, casts, crystals, epithelial cells, bacteria). Urinalysis should occur every 12 months.
- q *Should be performed predose.*
- r Actual PK sampling times must be documented. Actual date and time of study drug administration for the preceding two doses (except on Visit 1) must be documented in the eCRF.
- s Separate whole blood samples for SMN protein and SMN2 mRNA assessment. Please refer to Section 4.4.8.1.
- t Serum sample for fluid biomarkers. Please refer to Section 4.4.8.1.2.
- u In case it was not possible to collect *the baseline* sample during Visit 1, a sample for clinical genotyping should be drawn at the next visit. Please refer to Section 4.4.8.2.
- v ECG should be performed at screening and Visit 2 and then yearly from start of treatment.
- w *If dose increase visit is performed at a scheduled visit, ECG does not need to be performed since a 24-hour Holter ECG monitoring is being performed.*
- x Please refer to Section 4.4.10 for age-specific assessment and details. Complete before all other assessments during the study visit.
- y Please refer to Section 4.4.11 for details on the Caregiver-Reported Outcomes.

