2. STUDY DESIGN

Study BN29854 is a phase II, multicenter, open-label, single arm study to evaluate the long-term safety, tolerability and effectiveness of olesoxime (Roche No. RO7090919) 10mg/kg q.d. in patients with SMA who previously participated in one of the following two studies:

- Open-label phase Ib, dose-ranged, single and multiple dose study to assess safety and pharmacokinetics of olesoxime in 6-25 year old SMA patients (Trophos No. TRO19622CLEQ1115-1, Roche No. WP29845), and
- Phase II multicenter, randomized, adaptive, double-blind, placebo controlled study to assess safety and efficacy of olesoxime in 3-25 year old Type 2 or non-ambulatory Type 3 SMA patients (Trophos No. TRO19622CLEQ1275-1, Roche No. WN29836).

The study will consist of historical data collection, screening, treatment and safety follow-up periods. Patient visits will occur at 13, 26, 39 and 52 weeks and every 26 weeks thereafter for medical examinations, as well as safety and efficacy assessments. In addition, patients and their treating physicians will be requested to provide data for the period between the patients' last visit in the previous Trophos study and the screening period of study BN29854. Enrollment in the open-label treatment phase of the study is independent from the historical data collection, and a separate Informed Consent Form is required for each part. Patients (or their legal representatives) who do not consent to the historical data collection are still eligible to participate in the treatment phase of the study, and vice versa. The analysis methods that will be used for the historical data will be reported in a separate statistical analysis plan (SAP).

The study will continue until olesoxime is commercially available in the patient's country, or as per local regulation, or per the Sponsor's decision to terminate the olesoxime program for SMA, but will not exceed four years after the last patient was enrolled in the study. In the UK the study will last for a fixed period of three years after the last patient was enrolled.

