3. STUDY CONDUCT

3.1 RANDOMIZATION

BN29854 is a single arm, open-label study, and all patients receive olesoxime at 10mg/kg q.d.

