4.6.6 ECG

Actual values and change from baseline values will be summarized at each time-point using descriptive statistics for the following parameters: PR duration, QT duration, QRS duration, RR duration, QTc (Bazett) [QTcB], QTc (Fridericia) [QTcF].

ECG data will also be listed for patients with values outside the normal ranges and for patients with an ECG finding. The normal ranges will be based on the age of the patient at the time of the assessment. In addition, shift tables for each parameter (PR duration, QT duration, QRS duration, RR duration, QTcB, QTcF, T-wave, U-wave, sinus rhythm and overall interpretation) to compare the status at baseline to each time-point post-baseline and overall will be presented. The following normal ranges will be used:

Age (months)	PR Duration (ms)	QT Duration (ms)	QRS Duration (ms)	RR Duration (ms)	QTcF (ms)	QTcB (ms)
>24 and ≤144	80-160	260-390	40-90		380-450	300-450
>144	120-200	200-500	80-120	600-1500	380-450	300-450
>72 and ≤96				450-1000		
>96 and ≤144				600-1090		

The number and percentage of patients with an ECG finding at each time-point, (including the following atrioventricular [AV] blocks: 1st degree AV block, 2nd degree AV

block type I [Mobitz I], 2nd degree AV block type II [Mobitz II] and 3rd degree AV block), will also be summarized.

The number and percentage of patients with PR duration, QRS duration, QTcB and QTcF in the following ranges at each time-point will be presented:

ECG Parameter	Raw Value	Increase from Baseline
PR duration (ms)		
>24 and ≤144 months	≤ 160 > 160	
>144 months	≤ 200 > 200	
QRS duration (ms)		
>24 and ≤144 months	≤ 90 > 90	
>144 months	≤ 120 > 120	
QTcB (ms)		
	≤ 450	≤ 30
	> 450 and ≤ 480	> 30 and ≤ 60
	> 480 and ≤ 500	> 60
	> 500	
QTcF (ms)		
	≤ 450	≤ 30
	> 450 and ≤ 480	> 30 and ≤ 60
	> 480 and ≤ 500	> 60
	> 500	

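### SAP 4.6.6 classes QTc, but not PR or QRS, by increase from baseline, so PR lengthening inside the age-specific normal range can go uncounted in a subset of patients

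*SAP*

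**What the plan says.** SAP 4.6.6 plans several ECG displays.

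- **Continuous summaries.** "Actual values and change from baseline values will be summarized at each time-point using descriptive statistics for the following parameters: PR duration", followed by QT, QRS, RR, QTcB and QTcF. No age split or age adjustment is stated.
- **Listings and shift tables.** These use age-specific normal ranges. For PR the range is 80–160 ms up to 144 months and 120–200 ms above. "The normal ranges will be based on the age of the patient at the time of the assessment".
- **ECG findings.** "The number and percentage of patients with an ECG finding at each time-point" is to be summarised, with AV block of every degree included.
- **Category table.** "The number and percentage of patients with PR duration, QRS duration, QTcB and QTcF in the following ranges at each time-point will be presented". QTcB and QTcF have four raw-value classes and three classes of increase (up to 30, over 30 to 60, over 60 ms). PR has one raw cut per age band (160 ms, then 200 ms), and so does QRS (90 ms, then 120 ms). The increase column is blank for both.

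On why the heart is watched, Protocol 2.1 puts effects on ECG parameters in the primary objective. Protocol 1.4 says: "Atrioventricular conduction abnormalities observed in dogs have not been observed to date in humans". The same section cites arrhythmias in dogs as the reason for Holter monitoring around the dose increase. On timing, the Schedule of Assessments notes: "ECG should be performed at screening and Visit 2 and then yearly from start of treatment".

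**The concern.** The categorical display is the one that counts individual patients with a notable ECG result. For QTc it counts both a high value and a large rise. For PR, the interval that reflects AV conduction, it counts only a high value, and the threshold moves up by 40 ms at the twelfth birthday.

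Two things are at stake. First, some patients could have appreciable PR lengthening and never enter an outlier count, because they started low in the range or moved to the higher limit. Second, in children who pass 144 months a shift-table entry may reflect the change of reference range and not a change in the ECG. The study has no concurrent control, and after the first treatment ECG the standard ECGs are yearly, so each patient's own baseline is the natural comparator.

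**Working it through.** The plan gives no numerical figure on this point to reproduce. The check is arithmetic on the SAP's own limits, followed by an illustration whose assumptions are labelled.

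**1. Largest PR rise that stays in the normal class** (upper limit at the later age minus lower limit at the earlier age):

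| Situation | Formula | Result |
|---|---|---|
| Stays at or below 144 months | 160 − 80 | 80 ms |
| Stays above 144 months | 200 − 120 | 80 ms |
| Passes 144 months | 200 − 80 | 120 ms |

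These are the extremes. More ordinary starting values: 150 ms before age 12 can reach 200 ms after it (+50 ms, 33%) and remain normal. A child at 150 ms who stays under 12 leaves the class once the rise exceeds 10 ms. So lengthening can be missed, but is not always missed.

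**2. Change of status with no change in PR.** Both limits rise by 40 ms at 144 months (200 − 160 and 120 − 80). A constant 170 ms goes from above range to normal; a constant 100 ms goes from normal to below range. A child who doubles from 100 to 200 ms across the birthday stays normal.

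**3. Can patients pass 144 months on study?** Yes. Parent-study entry was from age 3, treatment lasted 24 months, and the sampled patients were 2.4–4.0 years past their last dose at this study's baseline (Protocol 1.2.2). The youngest parent-study completers would be about 3 + 2 + 2.4 = 7.4 years old. A child of 8 followed for 4 years reaches 12. Follow-up is limited only by the rule that the study "but will not exceed four years after the last patient was enrolled in the study". The documents do not give the number who cross.

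**4. Share of affected patients the single cut would miss (assumed model).** Take baseline PR as normal with its mean at mid-range (120 or 160 ms) and SD 15 to 25 ms. None of this is in the documents. For a patient at or below the upper limit L at baseline whose PR rises by d, the chance of staying at or below L is Φ((L − d − μ)/σ) / Φ((L − μ)/σ). With L − μ = 40 ms in both bands:

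| Rise d | Still uncounted, same band |
|---|---|
| 20 ms | 83–91% |
| 30 ms | 69–75% |
| 40 ms | 50–53% |
| 60 ms | 9–22% |

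For patients passing 144 months, any rise up to 40 ms stays uncounted whatever the model, since 160 + 40 = 200. At 60 ms, 83–91% stay uncounted.

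**5. What the mean shows when only a subset is affected (assumed shares).** Mean shift = share affected × rise. If 5–10% of patients lengthen by 40 ms, the overall mean moves by 0.05 × 40 = 2 ms to 0.10 × 40 = 4 ms. Growth alone could move it as much: if 5–30% of patients pass age 12 and drift by 10–40 ms, the pooled mean moves by 0.05 × 10 = 0.5 ms to 0.30 × 40 = 12 ms with no drug effect. The documents give neither the share nor the drift.

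**The case against.** The strongest reply is that a general effect on AV conduction would not be hidden. A PR rise of 20 ms in every patient appears in the planned summary as a mean change of 20 ms. With an assumed SD of change of 10–15 ms and 50 patients, the standard error is 10/√50 = 1.4 to 15/√50 = 2.1 ms, so the shift is roughly 9 to 14 standard errors. That stands.

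So does the point on timing. The summaries are made at each time-point and the first on-treatment ECG is at Week 13, which leaves little room for growth. That time-point mostly informs on the original once-daily dose.

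Other provisions also count: AV blocks are tabulated, out-of-range values are listed, a central laboratory assesses all tracings (Protocol 9.4), and 24-hour Holter recordings are made before and 4 weeks after the dose increase (Protocol 4.4.9.1) and summarised (Protocol 6.6). None of these is defined by a patient's own change in PR, so they do not count in-range lengthening. A maximum or SD among the descriptive statistics might hint at a tail, but would not say how many patients are in it.

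A reader might infer that the plan studies the wrong interval, or that it would report no conduction effect when one exists. The documents support neither. The QTc classes take nothing away from PR, the protocol reports no AV conduction abnormality in humans, and the mean change and block counts remain. The blank cells may well be deliberate, since QRS is treated the same way, though no reason is given.

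**Conclusion.** The gap is real but narrow. The category table and shift tables can pass over PR lengthening that stays within the age-specific range, by up to 80 ms within a band and 120 ms across 144 months. They can also show a change of class caused only by age. What is exposed is lengthening in a subset of patients, which the mean dilutes, and long-term mean changes that pool growing children with adults. The growth problem does not apply to adults and is an inference from the SAP's own ranges.

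The limits in steps 1 and 2 follow directly from the SAP, on one reading: that the category table uses age at assessment, as the normal ranges do. The table does not repeat this. If it used baseline age, the crossing examples would hold for the listings and shift tables only. The percentages in step 4 and the mean shifts in step 5 rest on assumed values and only illustrate scale.

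This is a descriptive safety display, and the underlying data are collected either way. Severity: minor.

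**What to change.** In SAP 4.6.6:

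1. Fill the increase-from-baseline column for PR and QRS with classes, absolute or percentage, set in advance with the central ECG laboratory. Show them by dose at the time of assessment, as Protocol 6.6 already requires for ECG data. The SAP needs this carried in, since SAP 3.1 still reads "BN29854 is a single arm, open-label study, and all patients receive olesoxime at 10mg/kg q.d".
2. Present PR and QRS change from baseline by baseline age band (up to 144 months, above 144 months) as well as overall.
3. In the shift tables, flag or show separately the patients who pass 144 months after baseline. Do not hold them to the younger limit: that would mark values of 161–200 ms as abnormal when the SAP defines them as normal at that age.
4. State which age (baseline or assessment) the category table uses.

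These are reporting categories and carry no rule for treatment. The cost is a few table rows and some SAP wording, from data already collected. The downside is some false positives from ordinary PR variability and, in children, from growth; showing the increase classes beside the absolute ones and by age band keeps that visible.

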4.7 MISSING DATA

For the MFM and HFMS scales, if any individual item score contributing to the total/sub-score is missing, then that item will be set to zero if there is at least one non-missing item at the assessment. If all items are missing, then the total/sub-score will be set to missing.

No imputation will be performed for missing safety variables.

4.8 INTERIM ANALYSES

The Sponsor may choose to conduct interim efficacy or safety analyses to adapt to information that may emerge during the course of this study, or for submissions to health authorities. The interim analyses will be performed and interpreted by Sponsor study team personnel.

